7.2 Per Protocol

The per protocol (PP) population is a subset of the mITT, which will include those subjects who do not have major protocol violations likely to seriously affect the primary outcome of the study as judged by a masked evaluation prior to the unmasking of the study treatment. These subjects will be analyzed in accordance with the treatment they actually received, even if that treatment is different from the planned treatment. The analysis with PP population is secondary.

7.3 Safety

All subjects who receive at least one dose of study drug will be included in the safety population. These subjects will be analyzed in accordance with the treatment they actually received, even if that treatment is different from the planned treatment (i.e., in the event of a randomization or dispensing error, subjects in the safety population will be analyzed as treated). Safety will be analyzed using the safety population.

8. General Statistical Considerations

8.1 Unit of Analysis

[figure not shown]
The unit of analysis in this study will be the study eye for all ocular assessments. Both eyes are study eyes as each subject receives Active treatment in one eye and Placebo in the fellow eye. Non-ocular assessments will be presented at the subject level.

8.2 Missing or Inconclusive Data Handling

Missing data will not be imputed. For measurements of AHD, if the result is missing in one eye, then the result for the contralateral eye will be assumed to be missing at the same time point.

8.3 Definition of Baseline

Baseline values for all AHD (trabecular outflow facility, IOP, EVP) are the time-relevant measures at 13:00 and 16:00 hour time points on Day 1, Visit 2 (e.g., measurement at 13:00 hours at Visit 2 will be the baseline for the measurement at 13:00 hours on Day 8, Visit 3).

Baseline mean diurnal values for all AHD is defined as the average of 13:00 and 16:00 hour measurements on Day 1, Visit 2.

8.4 Data Analysis Conventions

All data analysis will be performed by . Statistical programming and analyses will be performed using SAS® Version 9.4 or higher. Output will be provided in rich text format (RTF) for tables and portable document format (PDF) for tables, listings, and figures using landscape orientation. All study data will be listed by subject, treatment, visit, and time point (as applicable) based on all randomized subjects unless otherwise specified.

All continuous study assessments will be summarized by treatment and visit (as applicable) using descriptive statistics (number of observations [n], mean, median, standard deviation, minimum, and maximum). All categorical study assessments will be summarized by treatment, visit, and time point(as applicable) using frequency counts and percentages.

All study data entered in the database will be listed by subject, visit, and time point (as applicable).

All statistical tests will be performed with a significance level of 5% (one-tailed). Where applicable, two-sided 90% and 95% CIs will be reported.

8.5 Adjustments for Multiplicity

No adjustments for multiplicity are planned.

9. Disposition of Subjects

The following disposition items will be summarized:

- The number and percentage of subjects in each analysis population
- The number and percentage of subjects who completed the study
- The number and percentage of subjects who withdrew from the study and the reasons for premature discontinuation
- The number and percentage of subjects with any major deviations

All percentages will use the number of subjects treated as the denominator, unless indicated otherwise.

In addition, subject disposition and protocol deviation listings will be provided.

10. Demographic and Pretreatment Variables

10.1 Demographic Variables

The demographic variables collected in this study include age, gender, race, and ethnicity. Subjects who record more than one race will be grouped into a single category denoted as multi-racial. Demographic variables will be summarized for all randomized subjects.

Age (years) will be summarized, overall and by treatment, using continuous descriptive statistics. Age will also be categorized as follows: <65 years and ≥65 years. Age will be reported in years and calculated using the following formula:

Age = (informed consent date - date of birth) / 365.25 truncated as an integer

The number and percentage of subjects will be presented, for age category, gender, race, and ethnicity.

A subject listing that includes all demographic variables will be provided.

10.2 Pretreatment Variables

Ophthalmoscopy (dilated) examination (Retina, Vitreous, Macula, Choroid, Optic nerve; graded as normal or abnormal and cup-disc ratio) will be conducted at screening only.

Central corneal thickness (µm) will be measured by ultrasound pachymetry in both eyes (mean of two readings per eye). The mean value will be used for enrollment criteria. Pachymetry within 1 week of screening are acceptable.

Gonioscopy will be performed to confirm that the iridocorneal angle is open, and that the subject does not have narrow angle glaucoma, which is an exclusion criteria for study participation. Gonioscopy may be taken up to three months (i.e., within 90 days) prior to enrollment of the subject.

Subject listings will be produced for ophthalmoscopy, pachymetry, and gonioscopy results.

11. Medical History and Concomitant Medications

[figure not shown]
11.1 Medical History

Significant medical history will be collected and any current underlying medical conditions, including those that began within the last 30 days and which may have resolved before screening must be recorded.

A listing of medical history will be generated.

11.2 Concomitant Medications

Concomitant medications that are taken within 30 days prior to screening and during the study will be recored in the CRF. Concomitant medications will be coded using the World Health Organization (WHO) Drug Dictionary, (Enhanced B2, March 2017) and summarized to the therapeutic drug class (Anatomical Therapeutic Chemical [ATC] 4 classification) and preferred name. If the ATC 4 classification is not provided, the next lowest classification that is provided in the coding dictionary will be used. The preferred name will be defined as the active ingredient; if the active ingredient is not provided or includes more than two ingredients (eg, multivitamins) then the drug name will be summarized as the preferred

name. Any uncoded terms will be summarized under the ATC classification and preferred name of "Uncoded."

Concomitant medications will be summarized for all randomized subjects. Medications will be tabulated for all subjects if non-ocular and for each treatment if ocular using frequencies and percentages. Subjects may have more than 1 medication per ATC text. At each level of subject summarization, a subject will be counted once if he/she reports 1 or more medications. Percentages will be based on the number of subjects in each treatment group. Listings of concomitant medications will be generated separately for ocular and non-ocular data.

12. Dosing Compliance and Treatment Exposure

12.1 Dosing Compliance

A subject listing of study drug administration (i.e., showing whether subject used study eye drops for all seven days or not) will be produced.

13. Efficacy Analyses

All efficacy analyses will be conducted using the mITT population. If mITT is different from PP population, then the analyses will be repeated for the PP population.

13.1 Primary Analysis

The primary efficacy endpoint is the mean change from baseline in mean diurnal trabecular outflow facility (average of 13:00 and 16:00 hour measurements) per treatment on Day 8. Baseline mean diurnal outflow facility is defined as the average of 13:00 and 16:00 hour measurements on Day 1, Visit 2.

The null and alternative hypotheses, based on the primary endpoint, are as follow:

H01: The difference between study eyes treated with Netarsudil Ophthalmic Solution 0.02% and study eyes treated with Placebo, in the mean change from baseline of mean diurnal trabecular outflow facility = 0 on Day 8.

H11: The difference between study eyes treated with Netarsudil Ophthalmic Solution 0.02% and study eyes treated with Placebo, in the mean change from baseline of mean diurnal trabecular outflow facility > 0 on Day 8.

The null hypothesis will be tested using a paired t-test with alpha=0.05. One-sided p-values, two-sided 90% confidence intervals (CI), and two-sided 95% CIs will be presented. The trabecular outflow facility will be summarized by treatment and visit/time point using continuous descriptive statistics (and listed by subject.

13.2 Secondary Analyses

The secondary efficacy endpoints include:

- Mean change from baseline in mean diurnal IOP (average of 13:00, and 16:00 hour measurements) and mean diurnal EVP (average of 13:00 and 16:00 hour measurements) per treatment on Day 8
- Mean diurnal values for all AHD (trabecular outflow facility, IOP, EVP) per treatment on Day 8
- Mean values for all AHD at the individual 13:00 and 16:00 hourtime points per treatment on Day 8
- Mean change from baseline for all AHD at the individual 13:00 and 16:00 hour time points per treatment on Day 8. Baseline individual time points are defined as the corresponding measurements on Day 1, Visit 2
- Percent (%) change from baseline in diurnal means for all AHD per treatment on Day 8
- Percent (%) change from baeline at the individual 13:00 and 16:00 time points for all AHD per treatment on Day

Mean change from baseline in mean diurnal IOP and EVP will be analyzed similarly to the primary endpoint.

Similar to the primary efficacy analysis, mean differences in diurnal means of AHD measures and mean differences at the individual time points will be tested with paired t-tests. One-sided p-values, two-sided 90% CIs, and two-sided 95% CIs will be presented. Means within each treatment comparing diurnal mean on Day 8 with baseline diurnal mean and comparing individual time points on Day 8 with the corresponding time points at baseline visit will also be tested using paired t-tests. The same inferential statistics will be presented for these.

Mean percent change from baseline in diurnal means of AHD measures and mean percent change from baseline in AHD measures at individual timepoints will be tested using paired t-tests. The same inferential statistics will be presented for these.

All secondary efficacy endpoints will be summarized by treatment and visit/time point using continuous descriptive statistics.

14. Exploratory Analyses

Not applicable.

15. Safety Analyses

All safety analyses will be conducted using the Safety population.

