**Key Exclusion Criteria**

Subjects meeting any of the following criteria during screening or qualification evaluations (e.g., at the time of randomization) will be excluded from entry into the study:

Ophthalmic:

1. Clinically significant ocular disease (eg, corneal edema, uveitis, severe keratoconjunctivitis sicca) which might interfere with interpretation of the study efficacy endpoints or with safety assessments, including subjects with glaucomatous damage so severe that washout of ocular hypotensive medications for one month is not judged to be safe by the Investigator
2. Pseudoexfoliation or pigment dispersion component glaucoma, history of angle closure glaucoma, or narrow angles (as assessed by the Investigator, e.g. Grade 2 or less, Shaffer Scale). Note: Previous laser peripheral iridotomy is NOT acceptable
3. Intraocular pressure  $\geq 30$  mmHg (unmedicated) in either eye (individuals who are excluded for this criterion are not allowed to attempt requalification)
4. A difference in IOP between eyes >4 mmHg (unmedicated) at any baseline time point
5. Use of more than two ocular hypotensive medications within 30 days of screening. Note: fixed dose combination medications, for the purpose of this exclusion criterion, count as two medications
6. Known hypersensitivity to any component of the formulation (e.g., benzalkonium chloride, etc.), or to topical anesthetic.
7. Previous glaucoma intraocular surgery or glaucoma laser procedures in either eye
8. Keratorefractive surgery in either eye (e.g., radial keratotomy, PRK, LASIK, corneal cross-linking, etc.)
9. Report of ocular trauma in either eye within the six months prior to screening, or ocular surgery or non-refractive laser treatment within the three months prior to screening
10. Recent or current evidence of ocular infection or inflammation in either eye. Current evidence of clinically significant blepharitis, conjunctivitis, or a history of herpes simplex or zoster keratitis in either eye at

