### 4.2 Inclusion Criteria

Subjects have to meet all of the following criteria at screening and qualification visits to enter into the study:

1. Must be 18 years of age or older
2. Diagnosis of POAG or OHT in both eyes (OAG in one eye and OHT in the fellow eye is acceptable)
3. Unmedicated (post-washout, or treatment-naïve) IOP >20 mmHg and <30 mmHg in both eyes at 08:00 hours, and >17 mmHg but <30 mmHg at 13:00 and 16:00 hours at the qualification (Day 1, baseline) visit
4. Corrected visual acuity in each eye +1.0 on the logMAR scale or better by ETDRS chart or its equivalent in each eye (equivalent to 20/200 or better Snellen visual acuity in each eye)
5. Be able and willing to provide signed informed consent and follow study instructions

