## 7.2 Treatment Period

### 7.2.1 Visit 2 (Day 1, Qualification/Baseline) Procedures

This visit should occur no more than 2 to 7 days following the Screening visit, if the subject is treatment-naïve, or following the appropriate washout time prescribed for the IOP-lowering medication(s) they were taking at screening ([Table 1](#)).

Individuals who do NOT meet the IOP requirements at any of the timepoints in this visit may return for up to 2 additional visits within 1 week of failing this visit. Individuals returning for an unscheduled visit within 1 week to re-attempt IOP qualification are required to ONLY re-measure IOP in both eyes.

Upon return of the requalification visit, such individuals' IOP measurements would need to qualify at all timepoints (08:00, 13:00, and 16:00)

Individuals who screen fail due to IOP being  $\geq 30$  mmHg in either eye (exclusion criterion) MAY NOT return for additional qualification visits.

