### **9.4.3 Efficacy Analysis**

The primary endpoint is the mean change from baseline in the mean diurnal trabecular outflow facility on Day 8. The null and alternative hypotheses, based on the primary variable are as follows:

H01: The difference between study eyes treated with Netarsudil Ophthalmic Solution 0.02% and study eyes treated with Placebo, in the mean change from baseline of mean diurnal trabecular outflow facility = 0 on Day 8.

H11: The difference between study eyes treated with Netarsudil Ophthalmic Solution 0.02% and study eyes treated with Placebo, in the mean change from baseline of mean diurnal trabecular outflow facility > 0 on Day 8.

The null hypothesis will be tested using a paired t-test with  $\alpha=0.05$ . One-sided p-values, two-sided 90% CIs, and two-sided 95% CIs will be presented.

Secondary AHD measures: IOP and EVP will be analyzed similarly to the primary endpoint.

Similar to the primary efficacy analysis, mean differences in diurnal means of AHD measures and mean differences at the individual time points will be tested with paired t-tests. One-sided p-values, two-sided 90% CIs, and two-sided 95% CIs will be presented. Means within each treatment comparing diurnal mean on Day 8 with baseline diurnal mean and comparing individual time points on Day 8 with the corresponding time points at baseline visit will also be tested using paired t-tests. The same inferential statistics will be presented for these.

Mean percent change from baseline in diurnal means of AHD measures and mean percent change from baseline in AHD measures at individual timepoints will be tested using paired t-tests. The same inferential statistics as for the primary endpoint will be presented for these.

All AHD measures will be summarized by treatment and visit/time point using descriptive statistics (n, mean, median, standard deviation, minimum, and maximum).

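### The Day 1 afternoon IOP readings both qualify a subject and serve as the IOP baseline, so the planned within-treatment Day 8 versus baseline IOP tests can show a fall without any drug effect

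*SAP*

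**What the plan says.** **Entry.** Protocol 4.2, criterion 3, requires unmedicated "IOP >20 mmHg and <30 mmHg in both eyes at 08:00 hours, and >17 mmHg but <30 mmHg at 13:00 and 16:00 hours". These limits apply on Day 1 (Visit 2), which doubles as the baseline visit. The synopsis also excludes "A difference in IOP between eyes >4 mmHg (unmedicated) at any baseline time point".

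**Repeat attempts.** Under Protocol 7.2.1, a subject who misses the IOP limits "may return for up to 2 additional visits within 1 week of failing this visit". A reading of 30 mmHg or more ends the attempts. On what is repeated: "Individuals returning for an unscheduled visit within 1 week to re-attempt IOP qualification are required to ONLY re-measure IOP in both eyes".

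**Baseline.** SAP 8.3: "Baseline mean diurnal values for all AHD is defined as the average of 13:00 and 16:00 hour measurements on Day 1, Visit 2". The single 13:00 and 16:00 readings are the baselines for those time points. The 08:00 reading qualifies the subject but does not enter the diurnal baseline.

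**Tests.** SAP 13.2 applies paired t-tests to "Means within each treatment comparing diurnal mean on Day 8 with baseline diurnal mean and comparing individual time points on Day 8" against the corresponding baseline. Protocol 9.4.3 plans the same and adds "The same inferential statistics will be presented for these", meaning one-sided p-values with 90% and 95% confidence intervals. SAP 8.4 sets the level: "All statistical tests will be performed with a significance level of 5% (one-tailed". Neither document mentions regression to the mean or labels these tests descriptive.

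**The concern.** A reading that clears a floor does so partly because the eye's pressure is high and partly because that day or that reading happened to be high. The second part does not persist to Day 8. If the same reading is the baseline, the expected change is negative even with an inert drop. The between-eye comparison cancels this, because both eyes pass the same rule and the treated eye is randomized. The within-eye comparison does not.

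Two readings of the results are at stake. A significant fall in the netarsudil eye would mix drug effect with selection. A significant fall in the placebo eye could be taken for a vehicle or contralateral effect, although Protocol 1.3 justifies the paired design by a minimal contralateral effect.

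**Working it through.** **The plan's own figures.** None concerns IOP. The sample-size section is for outflow facility and reproduces: SD of the difference = sqrt(2 × 0.06² × (1 − 0.4)) = 0.0657, stated as 0.07. With a difference of 0.08, n = 16 and one-sided 5%, power is 99.7%, consistent with the stated figure above 95%. 16/0.8 = 20 randomized. I use n = 16 below.

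**Model.** Reading = subject and eye level + visit deviation v + reading error e. With no drug effect and an independent Day 8 visit:

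expected change = −E[v + mean(e at 13:00, e at 16:00), given that the subject qualified].

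The floors make the conditional expectation positive, so the change is negative. The 30 mmHg cap pulls the other way.

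**From the documents:** the floors and cap in both eyes, the 4 mmHg between-eye limit, one or three attempts, no return after 30 mmHg or more, the 13:00/16:00 mean as baseline, and a one-sided 5% paired t-test.

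**Assumed, because the documents give no values:** candidate-pool 08:00 mean 20 to 26 mmHg, between-subject SD 3, eye SD 1, drop of 2 mmHg from 08:00 to the afternoon, visit SD 0 to 2, reading SD 1 to 1.5. The tested direction for IOP is taken to be a fall, which the SAP does not state.

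**Result.** Simulated placebo-eye mean change (mmHg) and rejection rate, no drug, n = 16, no responder filter. The three-attempt column assumes that the requalifying visit is the baseline.

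| Pool mean | Visit SD / reading SD | One attempt | Three attempts |
|---|---|---|---|
| 20 | 1.5 / 1.5 | −0.71, 29% | −0.90, 39% |
| 20 | 2 / 1.5 | −1.10, 40% | −1.34, 52% |
| 22 | 1 / 1 | −0.18, 11% | −0.28, 15% |
| 22 | 2 / 1.5 | −0.66, 21% | −0.87, 29% |
| 24 | 1 / 1 | −0.06, 7% | −0.12, 9% |
| 24 | 2 / 1.5 | −0.24, 9% | −0.42, 13% |
| 26 | 2 / 1.5 | +0.16, 3% | +0.02, 5% |

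Other settings with pool means of 20 to 24 gave one-attempt rates down to 6%. With visit SD 0 the rate is 5% to 7%.

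**Hand check of the first row.** Ignoring the effect of selection on the SD, the SD of the change = sqrt(2 × (1.5² + 1.5²/2)) = sqrt(6.75) = 2.60. Its standard error = 2.60/√16 = 0.65, so the noncentrality is 0.71/0.65 = 1.09. A one-sided 5% t-test on 15 df then rejects in about 27% of trials, against 29% simulated.

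**Which visit is the baseline.** If a failed first visit stays the baseline for requalified subjects, the rate is about 4% to 9% at pool means of 20 to 24.

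**Between-eye IOP test.** Under the entry rule alone it rejects in 4.8% to 5.2% of trials.

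**The planned analysis set.** SAP 13 runs all efficacy tests in mITT, which keeps only subjects whose netarsudil eye fell by at least 2 mmHg. With that filter and no drug effect, the netarsudil-eye test rejects in 100% of trials. The placebo-eye test rejects in about 95% or more when visit SD is 1 to 2 (8% to 11% when it is 0), and the between-eye IOP test rejects in 33% to 100%.

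**The case against.** **The size is assumed.** This stands. The documents fix the mechanism but not its magnitude. A reader might infer that the 5% level is certainly exceeded. It need not be: the excess disappears at a pool mean of 26 mmHg, where the cap offsets the floors, and nearly so when visit-to-visit variation is negligible.

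**Three attempts forming the baseline is not written.** This stands too. Baseline is always Day 1, Visit 2, and a re-attempt is called an unscheduled visit at which only IOP must be repeated. Against that, criterion 3 sets its limits on the Day 1 baseline visit, randomization closes that visit, dosing starts the next morning, and Visit 3 comes 7 days after Visit 2. This timeline fits the requalifying visit better. The text does not settle it, so the larger three-attempt figures are conditional.

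**The simulated rates are not those of the tests as planned.** Correct: the responder filter dominates those tests. The entry-rule problem is separate and would remain if the filter were removed.

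**Harm is limited.** The objectives and formal hypotheses are between-eye, and no success claim is attached to the within-treatment tests. Strictly, the t-test's null is zero mean change. If selected eyes do fall on average, rejecting it is correct, and the error lies in attributing the fall to treatment. This limits the severity but does not justify printing a p-value that invites that attribution.

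**Outflow facility.** A reader might infer from equation 1 in Protocol 1.1 that selecting high IOP also selects low measured facility, so that facility would drift upward. The documents do not support this. Facility is not an entry criterion, the equation has four independent variables, a high reading may be tonometry error, and no facility drift has been computed.

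**Conclusion.** The point holds for the within-treatment IOP tests only. The same 13:00 and 16:00 readings select the subject and form the baseline, and there is no concurrent control. Under assumed pool means of 20 to 24 mmHg and visit SD of 1 to 2 mmHg, the nominal 5% test rejects in about 6% to 40% of no-drug trials with one attempt. The rate is higher with three attempts if the requalifying visit supplies the baseline. Outside that range there may be no excess.

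The primary facility comparison is not put in question on this ground. A reader might also infer that the between-eye IOP comparison is safe as planned. That is true of the entry rule alone, but not in the responder-filtered mITT set, where that comparison is itself biased.

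**What to change.** 1. In SAP 13.2, Protocol 9.4.3 and the synopsis, drop the p-values for within-treatment Day 8 versus baseline IOP comparisons, both diurnal and by time point. Show the mean change with its 95% CI as descriptive, with a footnote that the baseline readings were also used to qualify subjects. An interval that excludes zero can be misread in the same way, so the footnote is needed.
2. In Protocol 7.2.1 and SAP 8.3, state which visit supplies the IOP baseline after requalification.
3. State that conclusions on IOP rest only on the between-eye difference in change, in all randomized subjects with data and not in the responder-filtered mITT set.

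No change to the facility tests is asked for on this ground. The cost is wording, a table footnote and an IOP table in the unfiltered set, with no new data, visits or subjects. The sponsor loses a supportive within-treatment p-value.
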